Statistical Methods:	
Efficacy Data from all subjects who complete at least the first 4 weeks of the study drug (placebo or active) will be included in the efficacy analysis. Subjects whose biomarkers (CSF or amyloid PET) are found to be unsupportive of AD after they enroll in the trial will be excluded from the efficacy analysis. Subjects who decline to have CSF or amyloid-PET imaging will not be excluded from the efficacy analysis.
 
Cognitive, behavioral and functional measures, as well as M/EEG epileptiform activity, power spectral density for different frequency bands, and MEG-I functional connectivity at study days 1, 29, 57, and 85 will be recorded and summarized. Descriptive statistics will be generated as appropriate (i.e., mean, median, range, and standard deviation for continuous data and frequency for categorical data).
 
Each treatment effect will be tested for the assumption of normality. If the data are not normally distributed, we will investigate transforming data so they are normally distributed or nonparametric options. If we choose parametric tests, significance testing will be performed using analysis of variance (ANOVA) for repeated measures with drug treatment (LEV or placebo) as the independent variable. Prior to this analysis, ANOVA will be used to analyze the effect of drug-placebo sequence and to compare group demographics and severity of dementia at baseline (MMSE and CDR-SOB); if any of these factors confound the relationship between the study drug and the outcome measure, then they will be included as covariates in the ANOVA model. If factors arise that limit the appropriateness of the repeated-measures ANOVA model, such as a large dropout rate or varying data collection time points causing imbalance of longitudinal data, we will substitute a linear mixed effects regression model to better fit the longitudinal data without the intrinsic constraints of the repeated-measures ANOVA framework (Fitzmaurice et al. 2004, Finucane et al. 2007). If a drug carryover effect is observed on an outcome measure between weeks 4 and 8, then we will analyze the initial 4 weeks of the study separately for this outcome measure. Analyses will be two-tailed except for analysis of epileptiform activity, which will be one-tailed based on our expectation that LEV will reduce epileptiform activity (Sanchez et al. 2012, Mintz et al. 2009). For all analyses, the null hypotheses will be rejected at $p < 0.05$.
 
For the exploratory whole-brain MEG-I functional connectivity analyses, corrections for multiple comparisons will be performed using a cluster correction with a cutoff level of 20 voxels, and p values thresholded to 0.01. If no significant voxels are found at this threshold, we will use a less stringent threshold of $p < 0.05$. A hierarchical validation analysis will be used to account for multiple cognitive, behavioral, and functional tests.

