9.12 MEG-I

Whole-brain alpha-band functional connectivity will be derived from MEG-imaging (MEG-I) using the 60-second artifact-free recording epoch that is selected for the MEG spectral analysis. MEG-I uses MEG sensor data with millisecond precision and applies source reconstruction algorithms to

overlay cortical oscillatory activity onto structural brain images. Source-space MEG-I reconstructions and functional connectivity metrics will be computed with the NUTMEG software suite (<http://nutmeg.berkeley.edu>). We will compute imaginary coherence, which is a reliable metric for functional connectivity with MEG reconstruction. Functional connectivity will measure the strength of coherence between a given region and the rest of the brain. We will perform an unbiased search for MEGI-functional connectivity deficits that correlate with specific cognitive, behavioral, and functional deficits. Refer to the referenced publication for details of the methodology (Hinkley et al. 2011).

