10.2 Statistical Analysis of Efficacy Data

Data from all subjects who complete at least the first 4 weeks of the study drug (placebo or active) will be included in the efficacy analysis. Subjects whose biomarkers (CSF or amyloid PET) are found to be unsupportive of AD after they enroll in the trial will be excluded from the efficacy analysis.

Cognitive, behavioral and functional measures, as well as M/EEG epileptiform activity, power spectral density for different frequency bands, neural activity during cognitive tasks, and MEG-I functional connectivity at study days 1, 29, 57, and 85 will be recorded and summarized. Descriptive statistics will be generated as appropriate (i.e., mean, median, range, and standard deviation for continuous data and frequency for categorical data).

Each treatment effect will be tested for the assumption of normality. If the data are not normally distributed, we will investigate transforming data so they are normally distributed or nonparametric options. If we choose parametric tests, significance testing will be performed using ANOVA for repeated measures with drug treatment (LEV or placebo) as the independent variable. Prior to this analysis, ANOVA will be used to analyze the effect of drug-placebo sequence and to compare group demographics and severity of dementia at baseline (MMSE and CDR-SOB); if any of these factors confound the relationship between the study drug and the outcome measure, then they will be included as covariates in the ANOVA model. If factors arise that limit the appropriateness of the repeated-measures ANOVA model, such as a large dropout rate or varying data collection time points causing imbalance of longitudinal data, we will substitute a linear mixed effects regression model to better fit the longitudinal data without the intrinsic constraints of the repeated-measures ANOVA framework (Fitzmaurice et al. 2004, Finucane et al. 2007). If a drug carryover effect is observed on an outcome measure between weeks 4 and 8, then we will analyze the initial 4 weeks of the study separately for this outcome measure. Analyses will be two-tailed except for analysis of epileptiform activity, which will be one-tailed based on our expectation that LEV will reduce

epileptiform activity (Sanchez et al. 2012, Mintz et al. 2009). For all analyses, the null hypotheses will be rejected at $p < 0.05$.

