For the Virtual Route Learning Task, we will measure total accuracy summed across trials 2 through 15 (max score = 210) and accuracy at the delay trials (max score = 15). We will also explore the trial-by-trial accuracy, error rates, learning rates and asymptotes. The preliminary data suggest a 2 parameter exponential model will provide a good fit for the learning data. We will compare estimated learning rates and asymptotes parameters using ANOVA for repeated measures with drug treatment (LEV or placebo) as the independent variable. However, if additional data collection suggests that simple slopes better summarize the data, then we will use linear mixed effects models. If we use linear mixed effects models and residuals are not normally distributed, we will use bootstrapping techniques to produce reliable standard errors.

For the whole-brain MEG-I functional connectivity analyses, neuropsychological, behavioral, and functional measures from each subject will be correlated with global connectivity values at each voxel using the Pearson's correlation. Corrections for multiple comparisons will be performed using a cluster correction with a cutoff level of 20 voxels, and p values thresholded to 0.01. If no significant voxels are found at this threshold, we will use a less stringent threshold of $p < 0.05$. A hierarchical validation analysis will be used to account for multiple cognitive, behavioral, and functional tests.

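### The fixed 20-voxel cutoff offered as the multiple-comparison correction for the exploratory MEG-I maps is not tied in the documents to voxel grid, smoothness or a target map-wise error

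*Combined protocol and SAP*

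**What the plan says.** Section 10.2 has each clinical measure "correlated with global connectivity values at each voxel using the Pearson's correlation". It then gives the rule for the resulting map: "Corrections for multiple comparisons will be performed using a cluster correction with a cutoff level of 20 voxels, and p values thresholded to 0.01". The Statistical Methods entry of the Protocol Synopsis repeats the rule ("corrections for multiple comparisons will be performed using a cluster correction with a cutoff level of 20 voxels") and labels the analysis exploratory. Both places relax the voxel threshold to p<0.05 if nothing is found at 0.01, and neither gives a new extent for that case.

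Section 9.12 describes a whole-brain search, names the software and the connectivity metric, and ends: "Refer to the referenced publication for details of the methodology". I found no voxel size, smoothing, smoothness estimate, number of voxels searched, adjacency rule, null distribution or target map-wise error in the documents.

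Section 10.2 also promises a hierarchical validation analysis to deal with the several cognitive, behavioral and functional tests.

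Section 2.3, objective 5, compares LEV with placebo on connectivity in the regions that correlate with 27 listed measures (items a to aa).

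**The concern.** A cluster-extent rule corrects for searching many voxels only if the extent is large enough that a null map seldom produces such a cluster. How large that is depends on the number of voxels searched, their size and the smoothness of the maps. A bare count carries none of this. Twenty voxels is 2.5 cm³ on a 5 mm grid (20 × 0.125 cm³), 10.2 cm³ on an 8 mm grid (20 × 0.512 cm³) and 20 cm³ on a 10 mm grid (20 × 1 cm³).

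The selected regions are where the drug comparison under objective 5 is then made. If the cutoff is too lenient for these maps, that comparison is made in regions that arose by chance. If it is too strict, true regions are never examined. In either case, calling the rule a correction tells readers that the map-wise error is controlled, and the documents do not show that.

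**Working it through.** The plan states no map-wise error for this rule, so there is no figure to reproduce. The check asks how often a map with no true association yields at least one cluster of 20 or more voxels.

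**Inputs from the documents.** Extent 20 voxels; voxel p<0.01; Pearson correlation; whole-brain search; two-tailed testing (Section 10.2: "Analyses will be two-tailed except for analysis of epileptiform activity"); 36 subjects planned (Section 3) with 10% dropout (Section 10.1), so 36 × 0.9 = 32.4. The main runs used N = 34, with N = 32 as a check.

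**Assumed inputs, because the documents give none.** Spherical search volume of 1,400 cm³ (1,200 cm³ as a check); voxel edge 5, 8 or 10 mm; Gaussian smoothness from FWHM 0 to 30 mm; clusters joined across faces, edges and corners (face-only as a check).

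**Method.** For each null map, correlate a random score with N independent smoothed noise fields, convert by t = r·√[(N−2)/(1−r²)], apply the two-sided threshold with N−2 degrees of freedom, and find the largest same-sign cluster. Each setting used 72 to 506 maps.

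**Per-map false-positive rate of the stated rule, p<0.01, N = 34, 1,400 cm³:**

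| Voxel edge | Voxels in mask | FWHM 10 mm | 12 mm | 15 mm | 20 mm | 25 mm | 30 mm |
|---|---|---|---|---|---|---|---|
| 5 mm | 11,075 | 5–6% | 29% | 64% | 84–87% | 87% | 90% |
| 8 mm | 2,777 | 0% | 0% | 0.3% | 6–8% | 21% | 30% |
| 10 mm | 1,365 | 0% | 0% | 0% | 0.5% | 4% | 10.5% |

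At FWHM 8 mm or less, all three grids gave 0%.

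**Precision.** The Monte Carlo standard error is √[p(1−p)/n]. For 86.6% on 292 maps it is √(0.866 × 0.134/292) = 2.0 points. For 5.9% on 253 maps it is √(0.059 × 0.941/253) = 1.5 points. The spread in the table is not simulation noise.

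**Sensitivity.** Face-only adjacency gives 86% at 5 mm / FWHM 20 mm. With 1,200 cm³ and N = 32 the same cell is 78%. A separate simulation (N = 33, ellipsoidal mask, face-only) gave, at FWHM of 2, 3 and 4 voxels, 4%, 67% and 84% on about 12,900 voxels, and 0%, 18% and 33% on about 3,300. A further run gave 0%, 61% and 91% on about 12,900 voxels, and 1%, 19% and 33% on about 3,200. In voxel units these agree with the table: 10, 15 and 20 mm are 2, 3 and 4 voxels on the 5 mm grid, and 25 and 30 mm are 3.1 and 3.75 voxels on the 8 mm grid.

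**Extent that would give about 5% at p<0.01.**
- 5 mm voxels: about 21, 48 and 80 voxels at FWHM 10, 15 and 20 mm.
- 8 mm voxels: about 8 and 23 at FWHM 12 and 20 mm.
- 10 mm voxels: about 12 at FWHM 20 mm.

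The required cutoff thus ranges from about 8 to about 80, and no single count serves them all.

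**Fallback, p<0.05 with the same 20 voxels.** 72% and 98% at 5 mm with FWHM 8 and 10 mm; about 10% and 84% at 8 mm with FWHM 12 and 20 mm; about 34% at 10 mm with FWHM 20 mm. These are separate from the p<0.01 results, on which the point rests.

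**The case against.** The strongest reply is that Section 9.12 sends the reader to a publication for the method. The grid, the smoothing and even the basis for 20 voxels may be there. That stands as a limit: one can say that the protocol does not state the basis, not that none exists. It does not close the point, because the plan itself neither links the count to these maps nor names a target error.

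Second, the analysis is exploratory, and no primary or secondary conclusion depends on it. That is right, and it sets the weight of the point.

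Third, the hierarchical validation step might be thought to cover the matter. As worded, it addresses the multiple clinical measures, not the voxels within one map.

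Several stronger readings are tempting and are not supported:

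- A reader might infer that this trial's maps carry an error above 80%. That needs a fine grid with very smooth maps, and neither property is documented.
- A reader might infer that smooth null maps usually yield a region. On grids of about 3,300 voxels or fewer the rate never exceeded about 33%.
- A reader might multiply by 27 and expect about 5 false maps (27 × 0.18 = 4.9) or 18 (27 × 0.67 = 18.1). Those counts require that none of the 27 measures correlates with connectivity anywhere, and they ignore the hierarchical step.
- A reader might infer that the LEV-versus-placebo contrast is itself biased. A falsely selected region misdirects where that contrast is examined. Inflation of the contrast within the region has not been shown.

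**Conclusion.** The point holds for the exploratory MEG-I maps: the rule cannot be relied on as a correction, because one fixed count does not hold map-wise error near 5% across the settings examined. At p<0.01 the per-map rate is about 0% to 30% with 8 to 10 mm voxels, and about 0% to over 80% with 5 mm voxels. It is close to nominal at some combinations, such as 5 mm with FWHM 10 mm, and very conservative at others. These figures rest on assumed grids, smoothness and search volume and on Gaussian null fields; the trial's actual rate is unknown from the documents. What is at stake is how far any reported MEG-I region, and the choice of where to examine LEV under objective 5, can be trusted.

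**What to change.** Replace the fixed 20 voxels, in Section 10.2 and in the Synopsis, with a cutoff calibrated to these maps:

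1. State which visit supplies the map for each subject. Recordings are made on days 1, 29, 57 and 85, the plan does not say which is correlated, and the permutation below needs one map per subject.
2. For each measure, permute subjects' scores at least 1,000 times and record the largest cluster at the voxel threshold in use.
3. Keep only clusters above the 95th percentile of that distribution, and report the cutoff with each map.
4. If the p<0.05 fallback is kept, recalibrate the cutoff at that threshold.

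Simulation from the estimated smoothness of the maps would be an acceptable alternative, but permutation avoids having to assume the grid or smoothness.

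The cost is SAP wording and computing time, with no new data or visits. Some small clusters may no longer be reported. On rough maps or coarse grids the calibrated cutoff could fall below 20 and recover regions that the present rule would miss.

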Criteria for Evaluation:	
Primary Endpoints The efficacy of LEV to improve executive function (NIH EXAMINER) in patients with AD is the primary endpoint for this trial.
 
Secondary Endpoint The efficacy of LEV to suppress epileptiform activity (M/EEG), to improve cognitive function (Stroop interference naming and ADAS-cog), and to improve the degree of disability (CDR-SOB, ADCS-ADL, and ADCS-CGIC) and behavior (NPI) in patients with AD are the secondary endpoints for this trial.
 
Exploratory Endpoints We have the following exploratory endpoints for patients with AD:
 
 1. Effects of LEV on learning and memory using a computerized Virtual Route Learning Test. 2. Effects of LEV on Stroop color naming correct, Stroop color naming errors (uncorrected and self-corrected), and Stroop interference naming errors (uncorrected and self-corrected), and subcomponents of the ADAS-cog (learning and memory, language, constructional praxis, ideational praxis, and orientation). 3. Effect of LEV on clinical fluctuations using two standardized scales (Walker et al. 2000). 4. Effect of LEV on MEG power spectrum (delta, theta, alpha, beta and gamma activity) measures during rest and neural activity during cognitive stimulation. 5. Effect of LEV on MEG functional connectivity measures in brain regions that correlate with performance on NIH EXAMINER (composite and each component), ADAS-cog (composite and each component), Stroop Test, Virtual Route Learning Test with 4-hour recall, Clinician Assessment of Fluctuation, One Day Fluctuation Assessment, CDR-SOB, ADCS-ADL, ADCS-CGIC, and NPI (composite and each component). 6. Effect of LEV on serum prolactin levels. 7. Effects of LEV on all primary, secondary, and exploratory endpoints listed above in the following subgroups: 
 a. AD subjects with seizures or epileptiform activity, b. AD subjects without seizures or epileptiform activity, c. Early-onset AD (symptom onset < 65 years of age), d. Late-onset AD (symptom onset ≥ 65 years of age), e. AD-language (Gorno-Tempini et al. 2011), f. AD-PCA (Mendez et al. 2002), g. AD patients not classified as AD-language or AD-PCA, h. Very mild AD (MMSE of 24 and above), i. Mild to moderate AD (MMSE of 18 to 23), j. Subjects taking memantine, k. Subjects not taking memantine, l. Carriers the apolipoprotein E4 allele, and m. Noncarriers of the apolipoprotein E4 allele

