2.3 Exploratory Objectives

The exploratory objectives of this trial for patients with AD and seizures or epileptiform activity are as follows:

1. To explore the effects of LEV versus placebo on learning and memory using a computerized Virtual Route Learning Test.
2. To explore the effects of LEV versus placebo on the following outcomes measures:
 - a. Stroop color naming correct,
 - b. Stroop color naming errors (uncorrected and self-corrected),
 - c. Stroop interference naming errors (uncorrected and self-corrected), and
 - d. subcomponents of the ADAS-cog (learning and memory, language, constructional praxis, ideational praxis, and orientation).
3. To explore the effects of LEV versus placebo on clinical fluctuations using two standardized

scales (Walker et al. 2000):

- a. Clinician Assessment of Fluctuation, and
- b. One Day Fluctuation Assessment.

4. To explore the effect of LEV versus placebo on the following MEG power spectrum measures during rest and neural activity during cognitive stimulation:

- a. Delta band activity
- b. Theta band activity
- c. Alpha band activity
- d. Beta band activity
- e. Gamma band activity

5. To explore the effect of LEV versus placebo on the following magnetoencephalographic-imaging (MEG-I) functional connectivity measures in brain regions that correlate with performance on the following tasks:

- a. NIH EXAMINER composite score
- b. NIH EXAMINER – antisaccade
- c. NIH EXAMINER – set shifting
- d. NIH EXAMINER – flanker task
- e. NIH EXAMINER – dot counting
- f. NIH EXAMINER – spatial 1-back
- g. NIH EXAMINER – category fluency
- h. NIH EXAMINER – letter fluency
- i. ADAS-cog composite score
- j. ADAS-cog learning and memory
- k. ADAS-cog language
- l. ADAS-cog constructional praxis (visuospatial measure)
- m. ADAS-cog ideational praxis
- n. ADAS-cog orientation
- o. ADAS-cog 45-min word recall
- p. Stroop color naming correct
- q. Stroop color naming errors (uncorrected and self-corrected)
- r. Stroop interference naming correct
- s. Stroop interference naming errors (uncorrected and self-corrected)
- t. Virtual Route Learning Test
- u. Virtual Route 4-hour recall
- v. Clinician Assessment of Fluctuation
- w. One Day Fluctuation Assessment
- x. CDR-SOB
- y. ADCS-ADL
- z. ADCS-CGI
- aa. NPI

[figure not shown]
6. To explore the effect of LEV versus placebo on serum prolactin levels.

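### Exploratory MEG-I maps: if the relaxation to p < 0.05 is triggered when no 20-voxel cluster survives, the p 0.01 step does not lower the chance of a false finding in a map with no true association

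*Combined protocol and SAP*

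**What the plan says.** The last paragraph of section 10.2 correlates each neuropsychological, behavioral and functional measure with global connectivity at every voxel, using Pearson's r. It then states: "Corrections for multiple comparisons will be performed using a cluster correction with a cutoff level of 20 voxels, and p values thresholded to 0.01". The next sentence relaxes this: "If no significant voxels are found at this threshold, we will use a less stringent threshold of" p < 0.05. The Statistical Methods entry of the synopsis repeats both sentences and gives the status of the work: "For the exploratory whole-brain MEG-I functional connectivity analyses".

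Three neighbouring statements matter.

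- Section 10.2 adds: "A hierarchical validation analysis will be used to account for multiple cognitive, behavioral, and functional tests". The step is not described further.
- Section 9.12 says of the imaging method: "Refer to the referenced publication for details of the methodology".
- Exploratory objective 5 in section 2.3 compares LEV with placebo on "functional connectivity measures in brain regions that correlate with performance on the following tasks", so the maps select the regions for a treatment contrast.

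The plan states no error rate per map, no voxel count, no smoothness, no cluster connectivity and no basis for 20 voxels. It does not say whether the fallback is triggered by the absence of a cluster or of any single voxel, or whether 20 voxels still apply at p < 0.05.

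**The concern.** The fallback sentence directly follows the one that announces a correction for multiple comparisons, so a reader would take a fallback map as part of the corrected procedure. But a rule that tries a strict threshold and moves to a lenient one only on failure can lose the protection of the strict one. Failure at the strict threshold is the expected result when there is no association, which is where protection is needed.

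At stake is how the exploratory maps are interpreted. A region found by chance could be reported as a correlate of, say, an ADAS-cog component and then carried into objective 5. A LEV–placebo contrast in a region chosen by chance is uninformative about circuits related to performance.

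**Working it through.** The plan states no map-wise error rate, so there is no figure to reproduce. The check is a set argument followed by simulation.

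**Inputs from the documents.** Voxel thresholds 0.01 and 0.05, 20-voxel cutoff, Pearson correlation and two-tailed testing (section 10.2); 36 subjects (section 3); 10% dropout (section 10.1), so 36 × 0.9 = 32.4, run as 32.

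**Assumed.** Ellipsoid masks of 2,657 and 8,983 voxels; one observation per subject; Gaussian smoothness of FWHM 0 to 6 voxels; clusters of same-sign voxels joined by faces.

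**Step 1: nesting.** Let A be the event that a cluster of at least 20 voxels exists at p 0.01, and B the same at p < 0.05. Both use the same map, so every voxel that passes 0.01 also passes 0.05. Each A cluster therefore lies inside a B cluster at least as large, and A is a subset of B. For the cluster reading:

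P(rule declares a finding) = P(A) + P(not A, and B) = P(A or B) = P(B).

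This needs no assumption about voxel count, smoothness or sample size. It would fail only if the second step used a cutoff above 20 voxels, which the plan does not say. For a single voxel the same logic gives 0.01 + 0.04 = 0.05, not 0.01 + 0.05 = 0.06.

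**Step 2: size in maps with no true association.** n = 36; 500 maps per setting (smaller mask) or 400 (larger); Monte Carlo standard error at most √(0.5 × 0.5 / 400) = 2.5 points. Ranges run across the two masks.

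| FWHM (voxels) | 0.01 step alone | Whole rule, cluster reading | Points the fallback adds, single-voxel reading |
|---|---|---|---|
| 0–1 | 0% | 0% | 0 |
| 1.5 | 0% | 2–7% | 0 |
| 2 | 1–3% | 42–90% | 0 |
| 3 | 19–54% | 90–100% | 0 |
| 4 | 36–74% | 91–100% | 0–1.4 |
| 6 | 31–75% | 83–99.5% | 1.2–15.4 |

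The whole-rule rate equalled the p < 0.05 rate in every setting. With n = 32 and the smaller mask, the whole rule gave 2%, 47%, 92%, 92% and 85% at FWHM 1.5, 2, 3, 4 and 6.

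A second simulation used boxes of 12³ = 1,728 and 20³ = 8,000 voxels. The two rates were identical in all 16 settings, and no map had a 0.01 cluster without a 0.05 cluster. In the smaller box at n = 36 and smoothing SD 1.0 voxel (FWHM 2.355 × 1.0 ≈ 2.4), the 0.01 step alone gave 2.5% and the whole rule 52.4%.

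**Step 3: the single-voxel reading.** The fallback is then reached only if no voxel in the map passes 0.01. That occurred in 0% of null maps up to FWHM 2, 0–0.2% at FWHM 3, 0–5% at FWHM 4 and 1.5–30% at FWHM 6, hence the small last column.

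**Step 4: is 20 voxels the right cutoff?** For 5% per map, the cutoff needed was 14–19 voxels at p 0.01 and 39–52 at p < 0.05 (FWHM 2), and 33–44 and 93–141 (FWHM 3). No one cutoff served both thresholds.

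**Step 5: when a true association exists.** A true 81-voxel region was placed in the smaller mask. At r = 0.6 the fallback was used in 0–0.2% of maps and added under 1 point of false clusters elsewhere. At r = 0.4 it was used in 18–22%, and false clusters elsewhere rose from 1% to 10% (FWHM 2) and from 13% to 29% (FWHM 3).

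**The case against.** The strongest reply is that this is a pre-specified, openly stated relaxation in a hypothesis-generating analysis, and that the literal words refer to voxels, not clusters. On that wording the fallback hardly matters. Both points stand. The cluster reading remains the more natural one, because the preceding sentence defines significance through the cluster correction, but the text does not settle it.

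Three further points stand.

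- The absolute rates rest on assumptions. Section 9.12 refers method details to a publication that cannot be consulted here. Connectivity also matters: with 26-neighbour clusters in the smaller mask, the whole rule gave 8% rather than 2% at FWHM 1.5, and 60% rather than 44% at FWHM 2 (400 maps). The hierarchical validation step was not simulated; its stated purpose concerns the number of measures, not the voxel threshold.
- From about FWHM 3 the 20-voxel cutoff fails without any fallback, so deleting the fallback alone would not give 5%.
- The 0.01 step can still limit the extent of false regions. At FWHM 3 the share of voxels falsely flagged was 1.3–2.0% under the rule, against 2.7–2.8% at p < 0.05 throughout.

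A reader might infer more than the documents support. The equality does not hold conditionally on reaching the fallback: at FWHM 6 in the smaller mask, that chance is (83 − 31)/(100 − 31) ≈ 75%, below the 83% for the whole rule. Nor does choosing regions by chance by itself inflate the type I error of the LEV–placebo contrasts in objective 5. And the plan never says how a fallback map would be labelled, so reporting it as corrected is an inference from where the sentence stands.

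**Conclusion.** The point holds in a limited form. On the cluster reading, with 20 voxels kept, the two-step rule has exactly the false-finding rate of p < 0.05 with 20 voxels. That is a logical identity. It does not mean 5% per map, a rate the documents do not establish at either threshold.

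The size is conditional on the assumed masks, smoothness and face connectivity: 0% to 7% up to FWHM 1.5 voxels and roughly 42–100% from FWHM 2. On the single-voxel reading the fallback adds almost nothing unless maps are very smooth. On either reading, the uncalibrated 20-voxel cutoff is a problem by itself from about FWHM 3.

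The consequence is confined to the exploratory maps and the choice of regions for objective 5. It is worth correcting before the maps are analysed, but it does not threaten the trial's main results.

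**What to change.** In section 10.2 and in the Statistical Methods entry of the synopsis, replace the fallback sentence with: *If no cluster passes, none is declared for that measure; any p < 0.05 map is labelled uncorrected and descriptive and is not used to choose regions for exploratory objective 5.*

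State one voxel threshold in advance. The plan already has 0.01; 0.05 could also be used if its cutoff were calibrated, at the larger extents shown in the working. Replace the fixed 20 voxels by a cutoff set by permutation: shuffle subjects' scores against their maps, record the largest cluster each time, and take the value that gives 5% family-wise error per map.

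At p 0.01 in the smaller mask, simulated cutoffs of 14 voxels (FWHM 2) and 33 voxels (FWHM 3) gave 3.6% and 3.2% false maps in separate runs. A run with the cutoff set by score permutation held about 4–5%.

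The cost is wording in two places, some computing time and fewer declared regions. With a true r of 0.4 in 81 voxels (smaller mask), the calibrated cutoff finds the region in 84% of maps (FWHM 2) or 56% (FWHM 3), against 99% and 93% under the present rule. At r = 0.6 it finds it in 98–100%. The uncorrected map can still be shown, so nothing is hidden from later work.

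Which visit supplies the scores and recordings, which measures are mapped and what the hierarchical validation consists of are separate clarifications and not part of this point.
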